5.0 Study Procedures

Upon enrollment, we will collect patient characteristic at including 6-minute walk test, EKG, quality of life questionnaire, and NT-pro-BNP lab draw. In addition to this the CRT device will be interrogated and reprogrammed to a randomly assigned to BiV or RV pacing modality. They will be scheduled for a clinic visit in 3 months. During their return visit, they will undergo a 6-minute walk test, EKG, quality of life questionnaire (EQ-5D-3L Quality of life questionnaire), NT-pro-BNP lab draw, and device interrogation evaluating atrial arrhythmias and ventricular arrhythmias burden. Following completion of these tasks their CRT device will then be reprogrammed to the remaining pacing modality. This process will be repeated at 6-month appointment to complete a total of 3 months in each pacing modality.

The 6-minute walk test has been demonstrated to be an indicator of postoperative mortality in LVAD patients [3]. NT-pro-BNP can be a prognostic predictor of mortality in advanced heart failure. Device interrogation will be performed to evaluate lead impedance, determine quantity of tachyarrhythmias during testing period, and reprogram to next desired pacing modality.

6.0 Reporting of Adverse Events or Unanticipated Problems involving Risk to Participants or Others

Prior research has shown no difference between LVAD patients with and without CRT regarding mortality and hospitalizations [2]. There is no known significant risk above the inherent baseline risks of having a left ventricular device. Generally, CRT settings are maintained on BiV pacing though the pacing modality can be changed or turned off by the provider. However, recent research suggests that RV pacing may be beneficial to patients with improved functional status and quality of life [1]. While the exact mechanism for this benefit is unclear, we hope to mirror this result with BiV and RV pacing. The LVAD is controlling hemodynamic function and is not being altered for purposes of this study. There is no clear

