7.0 Statistical Considerations

Our primary endpoint is differences in 6-minute walk test between two pacing approaches. A sample size of a total n=24 subjects will allow us to detect an effect size 0.6 in a comparison of the two pacing methods with statistical power of 80% at the two-sided significance level of 0.05. We will randomize enrolled patients to either BiV or RV, and once they complete the 3 months of one modality, they will be switched to the other modality. To account for a patient attrition rate of 15%, we will randomize at least 28 patients.

For all subjects, we will assign study ids 1 to 28 to them in a sequential order based on time of enrollment (1 first, 28 last), such that each patient will undergo the pacing methods as ordered in the table below, where A stands BiV and B for RV. If more than 28 participants enroll, they will be assigned ids using consecutive integers from 29 and the statistician will create additional randomization assignments. The sequence (in terms of the order of pacing methods) will be as follows:

Pacing sequence AB: patients 2 6 7 8 11 13 15 16 17 20 22 24 25 27
Pacing sequence BA: patients 1 3 4 5 9 10 12 14 18 19 21 23 26 28

If patients elects to drop-out they will have the option to return to pre-study BiV pacing or to proceed to the next planned pacing assignment.

Analytical Plan: Briefly, descriptive data will be presented as mean \pm standard deviation (SD) and median and IQR as appropriate for continuous variables, or frequency and percentages for categorical variables. Statistical significance is set at 5% and nominal p-values are reported without multiple comparison adjustment. Regression analyses using linear mixed models or generalized estimating equations as appropriate for the outcome variable of interest will be used to assess the differences in pacing methods on each outcome variable while accounting for repeated measure correlations within each patient. Models will include subject (as a random effect), pacing method, period, sequence and residual treatment effect (carryover effects). The least square means as well as their confidence intervals for pacing method will be produced with and without carryover effects. Missing data are naturally handled by mixed effect models when data are missing at random. If GEE is used, multiple imputations will be employed before analysis.

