9.0 Follow-up and Record Retention

Patients will spend approximately 3 months in each of the pacing settings. Follow up will be scheduled to match their routine outpatient clinic follow appointments which occur every three months. At their routine clinical follow-up appointments, we will collect data at the 3- and 6-month marks following enrollment. At these visits, they will undergo 6-minute walk tests, device interrogation, NT-pro-BNP lab draw (N-terminal (NT)-pro hormone B-type natriuretic peptide), EKG, and quality of life screening questionnaire. Then the pacemaker device will be reprogrammed to the next pacing modality. Data will be kept in an encrypted Excel worksheet until the data is analyzed for publications.

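### The model with both sequence and carryover cannot estimate the pacing effect from the month-3 and month-6 visits, and no primary model for the 6-minute walk is named

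*Combined protocol and SAP*

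**What the plan says.** Section 7.0 (Statistical Considerations) randomises patients 1:1 to BiV then RV (AB) or RV then BiV (BA), with 14 study ids in each sequence. Patients change over after one period: "once they complete the 3 months of one modality, they will be switched to the other modality". Section 5.0 places the change at the month-3 visit, after the assessments: "Following completion of these tasks their CRT device will then be reprogrammed to the remaining pacing modality". No washout is described. Section 9.0 gives one on-treatment assessment per period: "we will collect data at the 3- and 6-month marks following enrollment". A 6-minute walk is also taken at enrolment (Section 5.0), but Section 7.0 does not say that it enters the model.

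On the analysis, Section 7.0 says: "Models will include subject (as a random effect), pacing method, period, sequence and residual treatment effect (carryover effects", and then: "The least square means as well as their confidence intervals for pacing method will be produced with and without carryover effects". The method is a linear mixed model or GEE, as suits the outcome. Neither carryover version is named as primary. The sample size statement is: "A sample size of a total n=24 subjects will allow us to detect an effect size 0.6", at 80% power and two-sided 5% significance.

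**The concern.** A two-sequence, two-period crossover cannot separate sequence, treatment and carryover from one response per period. A model holding all three is over-parameterised. Software will then either report the pacing means as non-estimable or silently drop a column, and which column goes determines what the pacing contrast means. If carryover goes, the result repeats the without-carryover analysis. If sequence goes, the result is a parallel-group comparison at month 3, and patients no longer serve as their own controls.

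The repair would therefore be chosen during analysis, possibly with data in view, and the possible repairs differ greatly in power. The plan also does not say which of its two promised pacing estimates answers the primary question.

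**Working it through.** **Inputs.** Sequences AB and BA, with responses at months 3 and 6 (Sections 5.0, 7.0 and 9.0). Effect size 0.6, n=24, two-sided 0.05 (Section 7.0). Assumed, because the documents do not give them: 12 completers per sequence; equal variance s² at each visit; equal within-patient correlation ρ between visits, shown from 0.3 to 0.9; and 0.6 expressed in units of the SD of within-patient differences.

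**The plan's own figure.** Noncentrality is 0.6 × √24 = 2.94. Noncentral t power is 80.4% on 23 df (paired t) and 80.2% on 22 df (with a period effect). The stated 80% is reproduced by the model without carryover.

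**Estimability.** Code BiV = +1, RV = −1, AB = +1 and BA = −1. Carryover takes the sign of the previous pacing mode and is 0 in the first period.

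| Cell | Intercept | Pacing | Period | Sequence | Carryover |
|---|---|---|---|---|---|
| AB, month 3 | 1 | 1 | −1 | 1 | 0 |
| AB, month 6 | 1 | −1 | 1 | 1 | 1 |
| BA, month 3 | 1 | −1 | −1 | −1 | 0 |
| BA, month 6 | 1 | 1 | 1 | −1 | −1 |

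Adding columns from left to right gives rank 1, 2, 3, 4, 4. In every row, carryover = (sequence − pacing)/2.

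The same result follows from the between-sequence differences (AB minus BA). Write σ for the sequence difference, τ for BiV minus RV, and λ for the differential carryover:

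- month 3: d1 = σ + τ
- month 6: d2 = σ − τ + λ

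That is two equations in three unknowns. The pacing contrast and both pacing means are not estimable; period is. A random subject effect does not help, because the aliasing is among fixed effects.

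**Possible repairs.**

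1. *Drop carryover.* The estimate is (d1 − d2)/2, with variance (1 − ρ)s²/12 and power 80.2%. Its expectation is τ − λ/2, so it is shifted by half of any differential carryover.
2. *Drop sequence.* The estimate is d1 alone, with variance 2s²/12 = s²/6. The variance ratio to repair 1 is 2/(1 − ρ). The standardised difference is 0.6√(2(1 − ρ)), tested 12 v 12 on 22 df.
3. *Add the enrolment walk as a third period, all patients on BiV.* Then d0 = σ and the model is full rank (6 of 6). The estimate is d1 − d0, with variance 2 × 2(1 − ρ)s²/12 = (1 − ρ)s²/3, which is 4 times repair 1 at every ρ. Noncentrality halves to 1.47, and power is 29% (22 df) to 30% (44 df).

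| ρ (assumed) | 0.3 | 0.5 | 0.7 | 0.8 | 0.9 |
|---|---|---|---|---|---|
| Repair 1 power | 80% | 80% | 80% | 80% | 80% |
| Repair 2 variance ratio | 2.86 | 4.0 | 6.67 | 10 | 20 |
| Repair 2 power | 38% | 29% | 19% | 14% | 10% |
| Period 1 adjusted for enrolment walk (21 df) | 41% | 37% | 33% | 32% | 30% |
| Repair 3 power | 29–30% | 29–30% | 29–30% | 29–30% | 29–30% |

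**Could the data show carryover to be absent?** The comparison of within-patient totals estimates d1 + d2 = 2σ + λ, so carryover is confounded with sequence. Suppose σ = 0 and λ is as large as τ. The standardised difference is then 0.6√((1 − ρ)/(1 + ρ)), and power on 22 df is 18%, 13%, 9%, 8% and 6% over the same correlations. A non-significant result would mean little.

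**The case against.** The strongest counter-argument is that Section 7.0 nowhere restricts the modelled responses to months 3 and 6. A walk is taken at enrolment, and the drop-out sentence in Section 7.0 treats BiV as the patients' pacing before the study. On that reading the enrolment walk is a third BiV period and the listed model is full rank. This stands as a possible repair, but not as a reading of the plan: Section 7.0 never makes the enrolment walk a modelled response. Section 6.0 also qualifies the starting state: "Generally, CRT settings are maintained on BiV pacing though the pacing modality can be changed or turned off by the provider". In any case the variance of the pacing difference would be four times larger.

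Second, the without-carryover analysis is promised too, can be computed and matches the sample size. A continuous walk distance points to the linear mixed model. That is correct, and it limits the damage: design, sample size and data collection are unaffected. It does not settle which result is primary.

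Third, the plan does not say which SD the 0.6 refers to. In between-patient SD units, repair 2 has 29% power at every correlation, while the crossover has 66%, 80% and 95% at correlations of 0.3, 0.5 and 0.7. The two readings coincide at 0.5, so reproducing 80% does not tell them apart. The gradient in repair 2 thus depends on the reading, but its large loss against the crossover does not. Adjusting period 1 for the enrolment walk softens that loss (41% to 30%) without removing it.

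**Conclusion.** The point holds. With the listed terms and one response per period, the with-carryover pacing means and intervals cannot be computed; this is algebra and rests on no assumption about variances. Which analysis decides the primary endpoint is left open. The stated 80% power is reproduced only without carryover. Every repair that yields a separate with-carryover pacing estimate has far less power: 38% to 10% with sequence dropped, or 29% to 30% with enrolment as a third period. Those figures assume 12 patients per sequence, equal correlation between visits, and 0.6 in units of the SD of within-patient differences. The without-carryover analysis is sound if differential carryover is negligible. This should be fixed before analysis, but it does not undermine the trial.

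**What to change.** In Section 7.0:

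- Name one primary analysis of the 6-minute walk: a linear mixed model on the month-3 and month-6 values, with pacing method, period and sequence as fixed effects, subject as random effect and no carryover term. Report the BiV minus RV difference with its 95% confidence interval.
- State that n=24 and 80% power apply to this model, and which SD the effect size 0.6 refers to.
- Delete the model that contains both sequence and carryover.
- If carryover is examined, compare within-patient totals between sequences descriptively, noting the confounding with sequence and the low power. A period-1 estimate adjusted for the enrolment walk may be shown as a low-power sensitivity estimate of the pacing effect, not as a carryover test.
- State that neither result will determine the choice of model.

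The cost is a few sentences of wording, with no change to design, sample size or data collection. The downside is that the primary model assumes negligible differential carryover. As no washout is described, the plan must argue this from measurement at the end of each 3-month period.

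### Enrollment values are collected but not modelled: a main-effect covariate would sharpen the promised carryover-adjusted estimate and leave the main within-patient estimate essentially unchanged

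*Combined protocol and SAP*

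**What the plan says.** All references are to the combined protocol and SAP.

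- **Section 5.0, at enrollment:** "Upon enrollment, we will collect patient characteristic at including 6-minute walk test, EKG, quality of life questionnaire, and NT-pro-BNP lab draw". The first device reprogramming belongs to the same visit.
- **Section 9.0, afterwards:** "we will collect data at the 3- and 6-month marks following enrollment". Each patient therefore has one outcome value per period and one enrollment value.
- **Section 7.0, model:** "Models will include subject (as a random effect), pacing method, period, sequence and residual treatment effect (carryover effects". No enrollment value is among the terms. The same section promises least-squares means and intervals for pacing method both with and without carryover, relies on missing at random in mixed models, and uses multiple imputation before any GEE analysis without naming the imputation variables.
- **Section 7.0, size:** "A sample size of a total n=24 subjects will allow us to detect an effect size 0.6", "with statistical power of 80% at the two-sided significance level of 0.05". Then: "To account for a patient attrition rate of 15%, we will randomize at least 28 patients".

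No section gives the enrollment values an analytic role beyond describing patients.

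**The concern.** A pre-treatment value of the outcome is often the strongest available predictor of later values, and this trial is small. Whether leaving it out matters depends on which of the two promised estimates is meant. If the pacing contrast is made within patients, each patient is already their own control and a single enrollment value has little to add. If it is made between patients, as happens once carryover is in the model, the full between-patient variance enters and the enrollment value could remove much of it. At stake is the width of an interval the plan commits to report and, to a smaller degree, the use made of patients who leave after period 1.

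**Working it through.** **Inputs.** From section 7.0: 24 completers, effect size 0.6, two-sided 0.05, 80% power, 28 randomized 14:14, 15% attrition. The effect size is read as the mean within-patient difference divided by the SD of those differences, since the plan does not name the SD. Assumed, because the documents give no value: within-patient correlation ρ of 0.5-0.8, constant over time unless stated, and enrollment values taken before the first reprogramming. The outcome SD is set to 1.

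**1. The plan's own figure.** The noncentrality is 0.6 × √24 = 2.94. Power is 80.4% with 23 degrees of freedom and 80.2% with 22, so n = 24 reproduces as a within-patient comparison. A parallel-group reading needs 44 per arm and does not fit. For attrition, 28 × 0.85 = 23.8, close to 24.

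**2. Estimate without carryover, complete pairs.** The contrast uses the difference between a patient's two periods, so SE = √(2(1 − ρ)/24). At ρ = 0.7 this is √(0.6/24) = 0.158. The enrollment value is the same in both rows of a patient, so its main effect cancels from the difference. A REML fit to simulated data confirmed this: estimate 0.04786 and SE 0.11222, with and without the covariate.

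Letting the slope differ by period does not help under constant correlation. In simulation at n = 24 it raised variance by about 4-5% and lowered power from about 80-81% to 78-79%.

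**3. Estimate without carryover, other conditions.**
- *Incomplete pairs.* With 24 complete pairs and 4 patients who have period 1 only (28 − 24, all assumed lost after month 3), variance falls by about 2-3% at ρ = 0.6-0.8.
- *Correlation that decays with time.* A gain with complete pairs requires more than a main effect. With period-specific slopes and known coefficients the reduction is ρ²(1 − ρ)/2: 0.36 × 0.4/2 = 7.2% at ρ = 0.6 and 0.64 × 0.2/2 = 6.4% at ρ = 0.8. With slopes estimated at n = 24, simulation leaves about 1-3%. A different model, with enrollment as a time-0 response and a known AR(1) covariance, gives 6-17% for ρ = 0.5-0.9, but it is not the random-subject model in the plan.

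**4. Is the carryover version estimable?** Two sequences by two periods give four cell means. Intercept, pacing, period, sequence and carryover are five fixed parameters, and the design matrix has rank 4. Adding the enrollment value and its period interaction gives rank 6 for 7 parameters, so the covariate does not remove the aliasing. Dropping the fixed sequence term leaves four parameters for four cells, and the pacing effect is then the period 1 difference between the two sequences.

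**5. Carryover-adjusted estimate, sequence dropped, 12 per sequence.** Without the covariate, SE = √(1/12 + 1/12) = 0.408. With it, the variance is multiplied by 1 − ρ². The planned effect in outcome SDs is 0.6 × √(2(1 − ρ)).

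| ρ | Planned effect | SE without | SE with | Variance cut (ρ²) | Power without | Power with |
|---|---|---|---|---|---|---|
| 0.5 | 0.600 | 0.408 | 0.354 | 25% | 29% | 35% |
| 0.6 | 0.537 | 0.408 | 0.327 | 36% | 24% | 33% |
| 0.7 | 0.465 | 0.408 | 0.292 | 49% | 19% | 32% |
| 0.8 | 0.379 | 0.408 | 0.245 | 64% | 14% | 30% |

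Simulations with the slope estimated give cuts of about 32-65% over ρ = 0.6-0.8, for example 47% at 0.7 and 62% at 0.8 in one set. An upper end just above the theoretical 64% should not be read as a real excess. On the theoretical SEs, interval width falls by 1 − √0.64 = 20% to 1 − √0.36 = 40%.

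**The case against.** The strongest case against is that leaving a single pre-period-1 value out of an AB/BA model is a defensible choice. The trial is powered on the within-patient contrast, where the covariate does nothing under the planned random-subject model. Nothing makes the carryover version primary, and it stays underpowered either way. The plan describes itself as small-scale work to inform larger trials. Adding a baseline-by-period term to every model would even cost a few percent of variance, and no covariate makes the quoted model with both sequence and carryover estimable.

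Most of this stands. It removes any claim of a general gain, rules out the interaction, and means the large reduction applies only after the sequence term is dropped. It does not answer the narrower point: the plan undertakes to report the carryover-adjusted interval, the data to narrow it are already collected, and a main effect does no harm to the main estimate.

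On missing data the argument is modest. A reader might infer that enrollment values are excluded from imputation. Section 7.0 lists no imputation variables, so it neither includes nor excludes them. Nothing in the documents shows that dropout depends on enrollment status, and the 15% attrition carries no timing.

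**Conclusion.** The point holds in limited form. For the main within-patient estimate the omission costs nothing with complete pairs and constant correlation, and a few percent of variance at most with period-1-only dropouts or decaying correlation. For the carryover-adjusted estimate, once estimable, the omission forgoes a variance reduction of roughly ρ², about 32-65% at an assumed ρ of 0.6-0.8 with 12 per sequence.

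Two stronger readings are tempting. One is that the primary analysis is needlessly imprecise; the arithmetic on the plan's own random-subject model does not support that. The other is that adjustment would make the carryover-adjusted estimate informative; power of about 30-35% says otherwise.

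The figures rest on the assumed correlation, on the effect size being in SDs of within-patient differences, and on enrollment values preceding the first reprogramming. This is a free improvement to a promised secondary output, not a defect in the main comparison.

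**What to change.** In section 7.0:

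- Add the enrollment value of the same outcome as a main-effect covariate in the models for 6-minute walk, NT-pro-BNP, EQ-5D-3L and QRS width, without a baseline-by-period interaction. State that the value is the one recorded before the first reprogramming.
- Include that value in any imputation model.
- In the carryover version, drop the fixed sequence term and say that the pacing effect is then a between-patient period 1 comparison with low power. The version without carryover can keep sequence.
- Leave tachyarrhythmia frequency out of this change: section 5.0 names arrhythmia burden only at the return visit, so no enrollment value is clearly available.

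The cost is one degree of freedom per model and a few sentences of SAP wording. No new data, visits or patients are needed.

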8.0 Privacy/Confidentiality Issues

No personal information will be published. Primary data will be collected via patient interview and stored electronically in REDCap. The storage location will be backed up automatically every day. Other data sources include lab data and device interrogations are automatically stored in patient's electronic medical records and will be merged with the primary data as needed. Quality assurance steps will include: testing of database by study team prior to moving to production mode. The following quality control methods will be used: single entry with random checks of accuracy and 2) extraction and cleaning of data that will be used for analysis every 6 months. Once patient data is initially collected, it will be de-identified before analysis.

9.0 Follow-up and Record Retention

Patients will spend approximately 3 months in each of the pacing settings. Follow up will be scheduled to match their routine outpatient clinic follow appointments which occur every three months. At their routine clinical follow-up appointments, we will collect data at the 3- and 6-month marks following enrollment. At these visits, they will undergo 6-minute walk tests, device interrogation, NT-pro-BNP lab draw (N-terminal (NT)-pro hormone B-type natriuretic peptide), EKG, and quality of life screening questionnaire. Then the pacemaker device will be reprogrammed to the next pacing modality. Data will be kept in an encrypted Excel worksheet until the data is analyzed for publications.

